4.1. Changes from Analyses Specified in the Protocol

The protocol states that the number of days free of mechanical ventilation at Day 29 will be compared between treatment groups using an analysis of covariance (ANCOVA), adjusting for age, and randomization stratification factor, *among survivors*. This has been clarified in [Section 7.2.2.1](#) of this SAP to be the number of days alive and free of mechanical ventilation; this represents a composite strategy for handling the intercurrent event of death.

The same modification applies to the duration of ICU stay at Day 29 *among survivors*, as well duration of hospitalization at Day 29 *among survivors*. These have been clarified in [Sections 7.2.2.2](#), [7.2.2.5](#), [9.4.5.2](#) and [9.4.5.3](#) of this SAP to be the number of days alive and not in the ICU and the number of days alive and not hospitalized, again representing a composite strategy for handling the intercurrent event of death.

Additional changes from the protocol are items 1, 2, and 4 given below in [Section 4.2](#) of this SAP. The analyses as specified in this SAP over-ride the protocol.

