7.2.2. Secondary Analyses

A closed testing procedure will be applied to control the type I error for the analyses of the primary and secondary endpoints at Day 29. If the primary endpoint is statistically significant in favor of ravulizumab, the secondary endpoints will be evaluated according to the following rank order:

1. Number of days free of mechanical ventilation at Day 29,
2. Duration of ICU stay at Day 29,
3. Change from baseline in SOFA score at Day 29,
4. Change from baseline in SpO₂/FiO₂ at Day 29,
5. Duration of hospitalization at Day 29.

The hypothesis testing will proceed from highest rank (#1) the number of days free of mechanical ventilation at Day 29 to the lowest rank (#5) duration of hospitalization at Day 29, and if statistical significance is not achieved at an endpoint ($p \geq 0.05$), then endpoints of lower rank will not be considered to be statistically significant. Confidence intervals and p-values will be presented for all secondary efficacy endpoints for descriptive purposes, regardless of the outcome of the closed testing procedure.

An additional secondary endpoint will be assessed beyond Day 29 regardless of the results of the closed testing procedure: Survival (based on all-cause mortality) at Day 60 and Day 90.

The PPS will be used in a sensitivity analysis for all secondary efficacy endpoints.

7.2.2.1. Number of Days Free of Mechanical Ventilation at Day 29

The number of days free of mechanical ventilation at Day 29 will be summarized by treatment group for all patients and by mortality. The number of days free of mechanical ventilation at Day 29 will be compared between treatment groups using an analysis of covariance (ANCOVA), adjusting for age and the randomization stratification factor, among survivors (ie, the number of days alive and free of mechanical ventilation).

Missing data will be imputed using a multiple imputation approach assuming the data are MAR and using a regression model with covariates for treatment group, the randomization stratification factor, age, sex and presence of a pre-existing condition at baseline (diabetes mellitus, obesity, respiratory condition, and/or coronary artery disease). Sensitivity analyses will include:

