- Worst-case scenario: missing days up to Day 29 for patients randomized to ravulizumab + BSC group will be considered as alive and not free of mechanical ventilation and missing days for patients randomized to BSC group will be considered as alive and free of mechanical ventilation for the remaining days up to Day 29
- All available data: no imputation of missing data
- Best-case scenario: missing days up to Day 29 for patients randomized to ravulizumab + BSC group will be considered as alive and free of mechanical ventilation and missing days for patients randomized to BSC group will be considered as alive and not free of mechanical ventilation for the remaining days up to Day 29
- Delta-adjustment tipping point analysis ([O’Kelly and Ratitch, 2014](#)): missing data for patients randomized to ravulizumab + BSC group are imputed by shifting the number of days alive and free for the observed patients downward by delta until any positive conclusion drawn from the primary analysis is reversed; refer to [Appendix 9.5.2.2.1](#) for additional details

7.2.2.2. Duration of ICU Stay at Day 29

The duration of ICU Stay at Day 29 will be summarized by treatment group for all patients and by mortality. Duration of ICU stay at Day 29 will be compared between the 2 treatment groups using an ANCOVA, adjusting for age and randomization stratification factor, among survivors (ie, the number of days alive and not in the ICU). Missing data will be handled as described for number of days free of mechanical ventilation at Day 29. The proportion of patients discharged

from the ICU will also be summarized and compared between the 2 treatment groups in a similar manner as the primary analysis of the primary endpoint.

7.2.2.3. Change from Baseline in SOFA Score at Day 29

Changes in SOFA score from Day 1 to Day 29 will be summarized by treatment group and study visit for all patients and by mortality.

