9.4.5. Definition of Durations

9.4.5.1. Number of Days Free of Mechanical Ventilation at Day 29

The number of days free of mechanical ventilation at Day 29 among survivors (ie, the number of days alive and free of mechanical ventilation) will be defined as:

Number of days alive – Number of days on mechanical ventilation, where

- Number of days alive = Earliest of Day 29 Visit Date or Disposition Date (for death) – Date of Day 1 + 1; set to 29 if > 29.

- Number of days on mechanical ventilation = sum of total number of days with mechanical ventilation from Date of Day 1 to Date of Day 29 Visit or Disposition Date (for death) ; set to 29 if > 29.

9.4.5.2. Duration of ICU Stay at Day 29

The duration of ICU stay at Day 29 among survivors (ie, the number of days alive and not in the ICU) will be defined as:

Number of days alive – Number of days in ICU, where

- Number of days alive is as defined in [Section 9.4.5.1](#).
- Number of days in ICU = sum of total number of days in ICU from Date of Day 1 to Earliest of Date of Day 29 Visit or Disposition Date (for death); set to 29 if > 29.

Number of days from first ICU date to Day 1 = Date of Day 1 – Date of first ICU entry; set to zero if negative.

9.4.5.3. Duration of Hospitalization at Day 29

The duration of hospitalization at Day 29 among survivors (ie, the number of days alive and not hospitalized) will be defined as:

Number of days alive – Number of days in hospital, where

- Number of days alive is as defined in [Section 9.4.5.1](#).
- Number of days in hospital = sum of total number of days in hospital from Date of Day 1 to Earliest of Date of Day 29 Visit or Disposition Date (for death); set to 29 if > 29.

Number of days from hospitalization to first dose date = Date of Day 1 – Date of hospitalization.

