9.5.2.2. SAS Code for the Secondary/Exploratory Efficacy Endpoints

9.5.2.2.1. Analysis of Covariance (ANCOVA)

For some secondary endpoints, an ANCOVA model will be used to compare the 2 treatment groups. The basic SAS code for this analysis is given by:

```
proc glm data = adef;  
class trt01p intub;  
model aval = trt01p age intub / solution;
```

```
lsmeans trt01p / cl diff stderr;  
run;
```

where aval is the number of days.

Missing data will be imputed using a multiple imputation approach assuming the data are MAR and using a regression model. The basic SAS code for this is:

```
Proc mi data=adeff out=outmi seed=1306528 nimpute=pctmissing round=. . . . 1 maximum=. . .  
.. 29 minimum=. . . . 1;  
class trt01p intub sex comorbid;  
var trt01p intub sex age comorbid aval;  
monotone reg(aval = trt01p intub sex age comorbid / details);  
run;
```

If an imputed value for a patient is less than the observed number of days until dropout, then the observed number will be used. The imputed data sets will then be analyzed by imputation using the ANCOVA method described above and the PROC MIANALYZE procedure will be used to generate valid statistical inferences about these parameters. The basic SAS code for this is:

```
Proc mianalyze data=parameterestimates;  
modeffects estimate;  
stderr stderr;  
run;
```

A sensitivity analysis will use a delta-adjustment tipping point approach where the missing data for patients randomized to ravulizumab + BSC group are imputed by shifting the number of days for the observed patients downward by delta. For each value of delta, the treatment effect will be determined, and the value of delta for which the nominal 2-sided p-value crosses 0.05 will be considered as the ‘tipping point’ in the sense that the positive conclusion drawn from the primary analysis is reversed. The basic SAS code for this is:

```
Proc mi data=adeff out=outmi seed=1306528 nimpute=pctmissing round=. . . . 1 maximum=. . .  
.. 29 minimum=. . . . 1;  
class trt01p intub sex comorbid;  
var trt01p intub sex age comorbid aval;  
monotone reg(aval = trt01p intub sex age comorbid / details);  
mmar adjust (aval / shift=delta adjustobs=(trt01p='Ravulizumab + BSC'));  
run;
```

where delta is the shift parameter for the imputed values of days for patients randomized to ravulizumab + BSC group.

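### Missing days alive and free of ventilation, ICU or hospital are drawn from a normal regression cut to 1–29, so a score of 0 cannot be imputed and imputed values run high on average

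*SAP*

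**What the plan says.** SAP Section 4.1 turns the three duration endpoints into counts of days alive and off support, and says of the ventilation count that "this represents a composite strategy for handling the intercurrent event of death". Section 9.4.5.1 gives the derivation: "Number of days alive – Number of days on mechanical ventilation, where" days alive run to the "Earliest of Day 29 Visit Date or Disposition Date (for death") and are capped at 29. The other term is built as "Number of days on mechanical ventilation = sum of total number of days with mechanical ventilation from Date of Day 1". Sections 9.4.5.2 and 9.4.5.3 do the same for ICU and hospital days.

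For missing values, Section 7.2.2.1 states: "Missing data will be imputed using a multiple imputation approach assuming the data are MAR and using a regression model with covariates" for treatment, stratum, age, sex and a pre-existing condition. It gives no bounds. For ICU and hospital days the SAP says: "Missing data will be handled as described for number of days free of mechanical ventilation at Day 29". Appendix 9.5.2.2.1 implements this as "monotone reg(aval = trt01p intub sex age comorbid / details", with imputed days rounded to whole numbers, a maximum of 29 and a minimum of 1. The tipping-point call repeats these options. One rule follows the imputation: "If an imputed value for a patient is less than the observed number of days until dropout, then the observed number will be used".

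**The concern.** The missing-at-random assumption means that a patient with unknown days should receive values distributed like those of similar observed patients. Every patient enters needing ventilation (Protocol Section 5.1) and planned mortality is 20% and 40%, so the observed distribution probably has a spike at 0. The coded draw excludes that value and spreads its mass over 1 to 29. The only post-imputation rule raises values, so it cannot restore a 0.

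These imputed values feed the main analysis of ranks 1, 2 and 5, and rank 1 must be won before any lower secondary endpoint can be claimed. In an open-label trial the two arms may well lose different numbers of patients.

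**Working it through.** **1. The plan's own figures.** The documents give no SD, power or missing rate for the day counts. The only figure to reproduce is the primary sample size (SAP Appendix 9.3: 60% vs 80%, one-sided 0.025, 90% power, 2:1). BSC n = [1.96·√(0.7333·0.2667·1.5) + 1.2816·√(0.6·0.4 + 0.8·0.2/2)]² / 0.2² = (1.0615 + 0.7250)² / 0.04 = 79.8, so 80 + 160 = 240 in a fixed design. The planned 81 + 162 = 243 has 90.4% fixed-design power, and 243/0.90 = 270. The survival rates and the 180 + 90 split are used below.

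**2. Attainable against imputable range.** Score = days alive − days on support.
- Dies on Day 10, ventilated on all 10 days: 10 − 10 = 0.
- Survives, ventilated on all 29 days: 29 − 29 = 0.
- Dies on Day 12 on ventilation, but with 2 days off it earlier: 12 − 10 = 2.

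The attainable minimum is 0 and the imputable minimum is 1, so P(imputed 0) = 0.

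**3. How common 0 may be.** P(0) = mortality × share of deaths scoring 0 + survival × share of survivors never off support. Both shares are assumptions. With 80% and 10%:
- ravulizumab: 0.20·0.80 + 0.80·0.10 = 0.24
- BSC: 0.40·0.80 + 0.60·0.10 = 0.38

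Taking 100% of deaths, or 25% of survivors, instead gives 24–36% and 38–47% over the settings tried.

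**4. Simulation.** 180 + 90 patients, the 80%/10% shares above, an assumed spread for positive scores, values missing at random within arm, no covariates, 10 imputations, 400 trials. Draws were repeated until the rounded value fell within the bounds. The rule that substitutes the observed count was not simulated. Entries are mean treatment differences in days.

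| Survival | Missing, ravulizumab/BSC | Truth | Bounds 1–29 | Bias | Bounds 0–29 | No bounds |
|---|---|---|---|---|---|---|
| 80/60% | 10/10% | 2.43 | 2.33 | −0.10 | 2.31 | 2.42 |
| 80/60% | 5/5% | 2.54 | 2.49 | −0.04 | 2.49 | 2.55 |
| 80/60% | 15/5% | 2.51 | 2.64 | +0.13 | 2.61 | 2.51 |
| 80/60% | 5/15% | 2.53 | 2.14 | −0.39 | 2.18 | 2.52 |
| 60/60% | 15/5% | 0.07 | 0.34 | +0.28 | 0.29 | 0.04 |

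Mean imputed values in the first row, ravulizumab/BSC: truth 10.40/7.95; bounds 1–29 12.46/11.06; bounds 0–29 12.09/10.81; no bounds 10.49/8.10. With a minimum of 0 only about 3% of imputed values are 0. Other simulations with different assumed distributions put the average upward shift between 1.6 and 3.3 days. In one of them 31–43% of missing patients truly scored 0; predictive mean matching imputed 0 for 32–43% and the coded method for none.

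**5. Why the bias follows missingness.** Bias ≈ m_R·s_R − m_B·s_B, where m is the missing fraction and s the mean upward shift per imputed patient.
- 10/10%: 0.10·(12.46 − 10.40) − 0.10·(11.06 − 7.95) = 0.206 − 0.311 = −0.105
- 5/15%: 0.05·(12.50 − 10.53) − 0.15·(11.17 − 7.95) = 0.099 − 0.483 = −0.384
- No effect, 15/5%: 0.15·(11.14 − 8.09) − 0.05·(11.18 − 7.71) = 0.458 − 0.174 = +0.284

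All three agree with the table. Under the planned effect the bias turns in favour of ravulizumab once its missing rate exceeds about 3.11/2.06 = 1.5 times that of BSC.

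**6. Effect on the test.**
- Equal missingness (10% per arm): estimate/SE was 2.02/1.20 = 1.68 as coded and 2.13/1.26 = 1.69 with predictive mean matching.
- Calibration (800 trials, 10% missing per arm): mean pooled SE 1.11 against an empirical SD of 1.11; with equal mortality, 1.09 against 1.02. Two-sided rejection under no effect was 3.1%, against 3.0% with predictive mean matching.
- Unequal missingness (15/5%, no effect): rejection in favour of ravulizumab was 4.8% and 5.6% in two simulations, against 2.7% and 2.9% with predictive mean matching. The nominal one-direction rate is 2.5%. The Monte Carlo error of the 5.6% is √(0.056·0.944/800), about 0.8 points.

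**The case against.** The strongest reply is that little is imputed. Known deaths are scored directly. Patients who are discharged or discontinued early are telephoned on Day 29 about survival, ventilation, ICU and hospital status (Protocol Sections 8.4.10 and 8.4.12). The all-available sensitivity analysis uses no imputation and was nearly unbiased in the simulation (2.43 against a truth of 2.43 at 10% missing per arm), and the worst- and best-case analyses can yield 0. This limits the size of the problem, and a distortion would show up against the all-available result. It does not correct the main analysis on which rank 1 is claimed.

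The bound also appears only in code labelled basic. As extracted, the rounding and minimum lists have five entries for six variables while the maximum list has six. That may be a PDF fault; reading the intended floor for days as 1 is an assumption.

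The no-effect simulations set survival equal in both arms. Rank 1 is tested only after the primary endpoint succeeds, so the practical risk is a trial with a survival gain but no gain in free days. That case was not simulated.

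A reader might infer three stronger points that do not hold:
- **Pooled standard errors too small.** They are lower than under predictive mean matching, but they match or exceed the estimator's own variability.
- **Every death on support scores 0.** Section 9.4.5 requires support on every day from Day 1.
- **The maximum for rank 1 should be 28.** Ventilation is an eligibility criterion, Screening can precede Day 1 by up to three days, and a patient weaned in between could reach 29.

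**Conclusion.** The point stands as a modest defect in the imputation for ranks 1, 2 and 5. A score that the SAP's own derivation allows cannot be imputed, and the truncated normal draw lifts imputed values by about 2 to 3 days on average. It does not follow that each individual imputed value is too high. Truncating a normal draw for an outcome with a spike at 0 does most of the damage; the floor of 1 rather than 0 adds little.

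With equal missingness the effect moves slightly towards the null and the decision barely changes. With unequal missingness the bias is about 0.1 to 0.4 days in favour of the arm with more missing data, subject to the break-even ratio above. It is conservative when BSC loses more patients and can inflate false positives at rank 1 when ravulizumab does. These sizes rest on assumed missing rates of 3–15% per arm, assumed shares scoring 0, and an assumed spread of positive scores. The primary endpoint and its sample size are unaffected.

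**What to change.** - **Main PROC MI call (Appendix 9.5.2.2.1) and Section 7.2.2.1:** replace the bounded linear regression with predictive mean matching on the same covariates, and say so in the text. Imputed values are then observed scores, 0 included.
- **Alternative:** keep the linear regression and remove the minimum and maximum. This restores the mean, but single draws can fall outside the attainable range, and the existing substitution rule would lift negative draws and bring back part of the shift.
- **Not sufficient:** changing the minimum to 0 alone. In one simulation the average shift fell only from 2.66 to 2.30 days.
- **Tipping-point call:** use the same base imputation, apply the delta shift, then floor the shifted values at 0, because a downward shift of a donor value of 0 would be negative.
- If any option lists remain, check that they match the variable list.

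The cost is a small change of wording and code before database lock, with no new data. Pooled standard errors would be slightly larger (1.26 against 1.20 in one simulation).

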Changes in SOFA score will be analyzed using a restricted maximum likelihood (REML)-based repeated measures approach (i.e. MMRM, [Mallinckrodt, 2008](#)) and all available longitudinal data. The model will include fixed effects for baseline SOFA score, age, randomization stratification factor, treatment group indicator, study day (Day 5, 10, 15, 22, 29), and study day by treatment group interaction. An unstructured covariance structure will be used to model the within patient errors. If this analysis fails to converge, the following structures will be tested and the final covariance structure will be determined by Akaike's information criterion (AIC): first-order autoregressive, compound symmetry, and Toeplitz. The Kenward-Roger approximation will be used to estimate denominator degrees of freedom. For patients who die, remaining values up to Day 29 will be imputed as a score of 24, the worst possible value.

A sensitivity analysis will be performed using a missing not at random (MNAR) mechanism for the missing data, where it will be assumed that unobserved outcomes for patients who discontinue early from the ravulizumab + BSC group will follow the trajectory of outcomes similar to the control group (BSC alone), taking into account observed values prior to discontinuation ([O'Kelly and Ratitch, 2014](#)). Patients discontinuing early from the BSC alone group will be assumed to have outcomes similar to the BSC alone patients who remain on their randomized treatment. Refer to [Appendix 9.5.2.2.2](#) for additional details.

7.2.2.4. Change from baseline in SpO₂/FiO₂ at Day 29

Changes in SpO₂/FiO₂ from Day 1 to Day 29 will be summarized daily by treatment group for all patients and by mortality.

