Changes in SpO₂/FiO₂ will be also be analyzed using a REML-based repeated measures approach (i.e. MMRM, [Mallinckrodt, 2008](#)) and all available longitudinal data. The model will include fixed effects for baseline SpO₂/FiO₂, age, randomization stratification factor, treatment group indicator, study day (Day 5, 10, 15, 22, 29), and study day by treatment group interaction. An unstructured covariance structure will be used to model the within patient errors. If this analysis fails to converge, the following structures will be tested and the final covariance structure will be determined by Akaike's information criterion (AIC): first-order autoregressive, compound symmetry, and Toeplitz. The Kenward-Roger approximation will be used to estimate denominator degrees of freedom. The daily post-baseline SpO₂/FiO₂ scores will be mapped to study day as described in [Appendix 9.4.6](#). For patients who die, remaining values up to Day 29 will be imputed as a score of 0, the worst possible value.

A sensitivity analysis will be performed using a control-based MNAR mechanism for the missing data as described for change from baseline in SOFA score at Day 29.

This analysis will be repeated for changes in PaO₂/FiO₂, where available, as a sensitivity analysis.

7.2.2.5. Duration of Hospitalization at Day 29

Duration of hospitalization at Day 29 will be analyzed in a similar manner as duration of ICU stay (ie, the number of days alive and not hospitalized). Missing data will be handled as described for number of days free of mechanical ventilation at Day 29. The proportion of patients discharged from the hospital will also be summarized and compared between the 2 treatment groups in a similar manner as the primary analysis of the primary endpoint.

7.2.2.6. Survival at Day 60 and Day 90

Survival (based on all-cause mortality) at Day 60 and Day 90 will be estimated using the KM method and compared using a log-rank test stratified by intubated or not intubated on Day 1. Hazard ratio and risk reduction will be summarized from a Cox proportional hazards model stratified by intubated or not intubated on Day 1. Confidence intervals (95%) will be presented for the survival estimates at Day 60 and Day 90 based on the complementary log-log transformation. KM curves for both treatment groups will be produced.

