9.5.2.2.2. Mixed Model for Repeated Measures (MMRM) Analysis

For some secondary endpoints, the analysis of changes over time involves an MMRM analysis. The basic SAS code for this analysis is given by:

```
proc mixed data = adeff method = reml;
  class subjid avisit trt01p intub;
  model chg = trt01p avisit trt01p*avisit base age intub / ddfm = kr solution;
  repeated avisit / type=un subject=subjid;
  lsmeans trt01p*avisit / cl diff;
  where 1 < avisitn;
run;
```

where trt01p is a variable that indicates the patient's randomized treatment group, subjid is the patient variable, avisit is the study day variable (0 representing Day 1), base is the value at baseline, age is patient age on Day 1, chg is the change from baseline at a particular visit, and intub is the randomization stratification factor.

The following illustrates the sensitivity analysis for missing data using the control-based approach, where for patients who discontinued treatment, responses after treatment discontinuation for both treatment groups will be imputed with multiple imputation methodology based on the response for BSC alone patients. Markov Chain Monte Carlo (MCMC) imputation method will be used to fill in the intermittent missing values under the assumption of MAR and generate a monotone pattern. Subsequently, multiple imputation will be performed at each visit sequentially, using a regression method obtained from BSC alone patients with terms for baseline score, the randomization stratification variable, and previous visits. After obtaining complete data sets for each visit, these complete data sets will be analyzed using MMRM analysis, and inferences from each complete data set will be combined to obtain an overall test statistic for treatment effect. The basic SAS code for this is:

```
Proc mi data=adefft out=monotone seed=1306528 nimpute=pctmissing;
  by trt01p;
  mcmc impute=monotone;
  var intubn base Day5 Day10 Day15 Day22 Day29;
run;
```

where trt01p is a variable that indicates the patient's randomized treatment group, base is the value at baseline, Day5 – Day29 are the changes from baseline at a particular visit, and intubn is a dummy variable for the randomization stratification factor.

The following is a partial SAS code for the BSC alone-based imputation at Day X:

```
Proc mi data=monotone out=outmi seed=1306539 nimpute=1;
  by _imputation_;
  class trt01p intub;
```

```
var intub base Day5 Day10 Day15 Day22 Day29;  

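### If the unstructured MMRM for SOFA or SpO2/FiO2 fails to converge, every listed fallback assumes one variance for all visits and would understate the Day 29 standard error

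*SAP*

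**What the plan says.** For SOFA, SAP 7.2.2.3 specifies a REML-based MMRM with baseline, age, stratum, treatment, "study day (Day 5, 10, 15, 22, 29), and study day by treatment group interaction". The primary covariance choice is flexible: "An unstructured covariance structure will be used to model the within patient errors". If that fit fails to converge, AIC selects from "first-order autoregressive, compound symmetry, and Toeplitz", and no heterogeneous-variance version is named. "The Kenward-Roger approximation will be used to estimate denominator degrees of freedom", and no empirical standard error is offered. The same section adds: "For patients who die, remaining values up to Day 29 will be imputed as a score of 24, the worst possible value".

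SAP 7.2.2.4 repeats the model, the fallback list and the degrees-of-freedom method for SpO2/FiO2, with its own death score: "For patients who die, remaining values up to Day 29 will be imputed as a score of 0, the worst possible value".

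The only MMRM code, in SAP 9.5.2.2.2, is "repeated avisit / type=un subject=subjid", with nothing for the fallback. Protocol 9.4.1.2 names the MMRM but no covariance structure. The two endpoints are ranks 3 and 4 of the closed testing procedure in SAP 7.2.2.

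**The concern.** A fallback is written in advance so that the analysis stays valid when the main model fails. Here all three candidates share one restriction, a common variance across visits, and the death rule in the same sections makes that restriction false. Each new death moves a patient to a score far from the survivors and keeps the patient there. While cumulative mortality is below 50%, p(1−p) rises with every death, and if survivors recover the gap to the death score widens as well. A common variance averages the quieter early visits into Day 29. AIC cannot repair this, because every candidate has the same restriction. Kenward-Roger does not repair it either, because it takes the variance structure as correct.

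At stake, if the branch is used, are the Day 29 confidence interval and nominal p-value for the two endpoints. The per-protocol, PaO2/FiO2 and control-based sensitivity analyses use the same model. PaO2/FiO2 is analysed only where available, so its data are sparser.

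**Working it through.** **The plan's own figure.** The documents give no SD, standard error or power for either MMRM. The figure that can be checked is the survival sample size (SAP 9.3). For 60% against 80%, one-sided 0.025, 90% power and 2:1 allocation, a fixed design with pooled variance needs 80 + 160 = 240 patients. The stated 243, with one interim analysis, is consistent with this, and 243/0.9 = 270.

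**Inputs from the documents.** Visits at Days 5, 10, 15, 22 and 29; death scores 24 and 0; 270 randomized 2:1; design mortality 40% and 20%, which pools to (2 × 20% + 40%)/3 = 26.7%.

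**Assumptions.** Death timing and the survivors' means and SDs are not in the documents. The worked SOFA case takes a constant hazard, a survivor mean falling linearly from 7 at Day 1 to 3 at Day 29, and a survivor SD of 3.

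**Step 1, variance by visit.** Ignoring baseline adjustment, with p = 1 − (1 − 0.267)^(t/29) and gap = 24 − survivor mean:

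variance(t) = p(1 − p) × gap² + (1 − p) × 3²

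| Day | p | gap | variance | SD |
|---|---|---|---|---|
| 5 | 0.052 | 17.57 | 23.8 | 4.9 |
| 10 | 0.102 | 18.29 | 38.6 | 6.2 |
| 15 | 0.148 | 19.00 | 53.3 | 7.3 |
| 22 | 0.210 | 20.00 | 73.5 | 8.6 |
| 29 | 0.267 | 21.00 | 92.9 | 9.6 |

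**Step 2, effect on the standard error.** A common-variance fit uses roughly the mean variance, 282.1/5 = 56.4.

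- SE ratio = √(56.4/92.9) = 0.78, so the Day 29 standard error is about 22% too small.
- Two-sided rejection at nominal 5% = 2 × [1 − Φ(1.96 × 0.78)], or about 13%.

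**Step 3, range.** The same formula was run over 72 scenarios: mortality 20% to 40%, late to very early deaths, and survivors flat, recovering, or recovering with shrinking SD.

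- SOFA: ratio 0.72 to 0.97, rejection 5.6% to 15.6%.
- SpO2/FiO2: ratio 0.73 to 0.99, rejection 5.2% to 15.4%.
- With very early deaths and flat survivors the shortfall is only 1% to 5%.
- Variance was largest at Day 29 in every scenario.

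**Step 4, REML simulation of the SAP model.** 270 patients, 2:1, 26.7% mortality in both arms, no treatment effect. Cells give model SE/empirical SE, then rejection.

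| Scenario (trials) | Unstructured | AR(1) | Toeplitz | Compound symmetry |
|---|---|---|---|---|
| SOFA, constant hazard (500) | 1.02, 4.6% | 0.80, 10.6% | 0.80, 10.6% | 0.80, 11.2% |
| SOFA, early deaths (250) | 1.03, 4.8% | 0.87, 9.2% | 0.87, 9.2% | 0.87, 9.6% |
| SOFA, discharged survivors missing (250) | 1.00, 6.4% | 0.74, 14.8% | 0.74, 14.4% | 0.71, 16.0% |
| SpO2/FiO2, constant hazard (250) | 1.00, 6.0% | 0.77, 12.8% | 0.77, 12.8% | 0.75, 12.8% |

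AIC chose only Toeplitz or AR(1); in the first row the split was 374 to 126. A shorter 250-trial run of that scenario gave fallback ratios of 0.84 to 0.85 and rejection of 10.4% to 10.8%, with unstructured at 1.08 and 2.8%. Three further SOFA simulations agree for evenly spread deaths:

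- 600 trials: 0.96/1.21 = 0.79, rejection 12%.
- 300 trials, Toeplitz: 0.80, rejection 12.7%.
- 150 trials: 0.82, rejection 14%. With early deaths the same check gave 0.92 and 8%.

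**Step 5, does the remedy work?**

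- Heterogeneous AR(1) alone, 400 trials: SE 6% too small, rejection about 8%.
- Heterogeneous Toeplitz or AR(1) alone, 300 trials: ratio about 0.95, rejection 5.7% to 6.7%.
- The same with a sandwich standard error: ratio 0.995 to 1.003, rejection 4.7% to 6.3% (simulation error about 1.3 points).
- Heterogeneous structures with a sandwich standard error, 150 trials per scenario: rejection about 3% to 5%.

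**The case against.** Three objections deserve weight.

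**The branch is a contingency.** A reader might infer that the Day 29 standard error in this trial is too small. The documents do not support that. The unstructured model comes first, it has 5 × 6/2 = 15 covariance parameters for about 270 patients, and deaths are filled in rather than missing. Non-convergence was not a problem in the simulations, and the unstructured test stayed close to nominal. This stands, and it sets the priority.

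**The hierarchy limits the confirmatory harm.** A reader might also take a 12% rejection rate as a 12% false-positive rate for ranks 3 and 4. SAP 7.2.2 rules that out: a confirmatory SOFA claim requires the primary endpoint and ranks 1 and 2 to succeed first. With no survival effect, the one-sided 0.025 test stops at least 97.5% of trials, so a false confirmatory SOFA claim occurs in at most 2.5%. If survival truly improves, the death score usually makes the SOFA null false too. At the design rates with BSC survivors at 3, the BSC mean is 0.4 × 24 + 0.6 × 3 = 11.4. Equality would need ravulizumab survivors at (11.4 − 4.8)/0.8 = 8.25. With equal survivors the difference is 0.2 × 21 = 4.2 points, and 4.2/1.21 gives z of about 3.5 even with a correct standard error. This stands as well. The confidence interval and nominal p-value, which are reported regardless of the hierarchy, would still be wrong.

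**The size is not fixed.** Protocol 4.2 notes that deaths often follow soon after symptoms begin, which points towards early deaths and a smaller error. So a range is needed, but the direction was the same throughout it.

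The control-based sensitivity analysis is not a safeguard. It changes the missing-data assumption and then fits the same MMRM.

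**Conclusion.** The point holds as a conditional one. If the unstructured fit fails, the listed fallbacks give a Day 29 standard error and confidence interval that are too small for both endpoints, and AIC cannot correct this. Across the assumed scenarios the standard error is about 1% to 28% too small, and the nominal 5% two-sided test rejects about 5% to 16% of the time. For SOFA with complete data this is about 11% to 14% with evenly spread deaths and about 8% to 9% with early deaths. These sizes rest on assumed death timing and survivor scores; only the mortality rates, visits, death scores and sample size come from the documents. They describe the nominal test and interval, not the confirmatory error rate, which the gate on the primary endpoint and ranks 1 and 2 also limits. Priority is low, because the branch should seldom be used.

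**What to change.** In SAP 7.2.2.3 and 7.2.2.4, replace the fallback list with heterogeneous Toeplitz, then heterogeneous AR(1), then heterogeneous compound symmetry, taking the first that converges. Whenever a fallback is used, base the Day 29 contrast on an empirical (sandwich) standard error. Both parts are needed, because the heterogeneous structures alone left a shortfall of about 5% to 6% in simulation. Add the fallback code to SAP 9.5.2.2.2.

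The cost is a sentence in each section and a keyword or two in the code. There are a few more covariance parameters: heterogeneous Toeplitz has 9 (5 variances and 4 correlations) against 5 for plain Toeplitz. It could itself fail where the unstructured fit fails; convergence of the new list was not studied, which is why the order ends with simpler structures. Kenward-Roger is not used with the sandwich standard error, so the SAP should name the degrees-of-freedom method for that branch. Data collection, sample size and the primary analysis are unaffected.
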